Due to delays on data processing from the Swedish data custodians, data became available for the planned analyses in December 2019. The validation questionnaires to GPs in the UK were eventually available electronically in February 2020. Very low response rate of GPs to questionnaires to validate SCD diagnosis, because of COVID-19 shut down in the UK, motivated a proposal that the validation questionnaires to the GPs in the UK would be sent out again in Q1 2021, aiming to improve the response rate. Continued COVID-19 related shut down in the UK necessitated further postponement of sending the validation questionnaires to GPs in the UK to Q4 2021. When approached on this matter in Q4 2021, the planning manager at CPRD explained that CPRD paused GP questionnaire studies until further notice due to the shortage of primary care clinical staff in the UK to continue focusing their resources on supporting COVID-19 activities. In Q2 2022, CPRD confirmed that they have reopened GP questionnaire services and suggested the study team to resume the validation questionnaires in Q4 2022 given CPRD's resources and current pipeline of work. In the protocol version 12.0, the MAH proposed to reopen the UK validation study in October 2022 until January 2023 with planned study report date in Q3 2023. In response to the MAH's proposal, in the preliminary assessment report for the PASS protocol amendment submission (3rd Oct 2022), PRAC requested the MAH to extend the UK observational period up to the most recent possible date in order to include all available data and to revise the data collection period in the milestones accordingly, without further postponement of the final report (Q3 2023). The MAH contacted CPRD to confirm next steps for data extraction and validation study rerun. CPRD required that the MAH submit a new protocol to the CPRD review committee before requesting the new datasets and re-running the validation study. This is due to the change of dataset from CRRD GOLD to CPRD GOLD and CPRD Aurum, and the change of the observational period. Of note, most practices have moved from CPRD GOLD to CPRD Aurum in the last few years, which makes the CPRD GOLD dataset much smaller. In parallel the MAH informed the EMA / PRAC Rapporteur on 31st March 2023, of the challenges faced due to the protocol update and the consequential impact to the final PASS CSR deliverable. The process from the submission of the protocol amendment until receiving datasets from CRPD is approximately 3-4 months. The MAH submitted a new protocol to CPRD in April 2023 and expected to receive approval and the new datasets in Q3 2023. The MAH proposed to identify the new SCD cases and controls from the new datasets first and reopen the UK validation study in Q4 2023 - Q1 2024 to validate the new cases and controls. However, due to delays in data access, the MAH received the latest CPRD GOLD and CPRD Aurum data cut in March 2024. The validation will be conducted in Q2-Q3 2024.

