6 MILESTONES

Table 1. Milestones

Milestone	Date
Start of data collection	February 2013 (Sweden) May 2013 (UK) September 2014 (Spain)

End of data collection	Electronic datasets: 
- Spain and Sweden: Data collected up to December 2018. Effective date when data up to December 2018 can be accessed (incorporating time for data access applications to be processed)- UK: the most recent HES and CPRD data available at the time of data access in 2024, i.e., 20 October 2023 for CPRD Aurum, 17 November 2023 for CPRD GOLD 31 March 2021 for HES APC 31 October 2020
------------------------	--

Milestone	Date
	for HES OP, 31 March 2020 for HES AE and 29 March 2021 for ONS death data. Validation: - UK: Q2-Q3 2024 - Spain: Q2 2020 Analytical dataset completely available: Q4 2024
Registration in the EU PAS register	September 2016
Study progress reports	With each PSUR
Interim reports	No
Final report of study results	Q4 2024
EMA submission	Q1 2025

Abbreviations: CPRD Clinical Practice Research Datalink; EU European Union; GP general practitioner; HES Hospital Episode Statistics; PAS post authorisation study; PSUR periodic safety update report; UK United Kingdom; NPR National Patient Register; PDR Prescription Drug Register

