9.2.1.4 TIME PERIODS AND DATES

The study period is determined by the launch date of linaclotide, subsequent uptake, and length of time required to accrue a non-trivial number of SCD cases (see case definition above, Section 9.3 *Variables* and Section 9.5 *Study Size* below). The study period starts on the date of linaclotide commercialisation in each of the countries: in Sweden on February 2013, in the UK on May 2013, and in Spain on September 2014.

The end of data collection has been extended to November 2023 in the UK, and December 2018 in Sweden and in Spain, so the study period will include 50 months in Spain, approximately 10 years in the UK and 68 months in Sweden for medical and prescription data accrual, each database's lag time (for collected data to be available in each database, estimated in up to eight months or until August 2019), and seven months for initial data management and additional data collection from GPs (Q3 2019 for Spain and Sweden, and currently planned until Q3 2024 for the UK). Due to delays experienced in accessing data from the Swedish authorities, version 7.0. of the protocol proposed to extend the final delivery of the final report until June 2020. This is because data from Sweden was not anticipated to become available until Q3-Q4 2019. Version 9.0 of the protocol proposed to extend the final delivery of the final report to June 2022. A very low response rate by the UK GPs to questionnaires

sent to them in Q1 2020 to validate SCD diagnosis was observed. This was possibly because of the shut down in the UK due to COVID-19 infections. A decision was made to resend the questionnaire in Q1 2021. The continued COVID-19 related shutdown in the UK necessitated further postponement of resending the questionnaire to GPs. MAH proposed to resend the questionnaires in Q4 2021. When approached on this matter in Q4 2021, the planning manager at CPRD explained that CPRD paused all GP questionnaire studies until further notice due to the shortage of primary care clinical staff in the UK to continue focusing their resources on supporting COVID-19 activities. Version 11.0 of the protocol proposed to re-open UK validation study in October 2022 until January 2023 with planned study report in Q3 2023.

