In response to the MAH's proposal, in the preliminary assessment report for the PASS protocol amendment submission (3rd Oct 2022), PRAC requested the MAH to extend the UK observational period up to the most recent possible date in order to include all available data and to revise the data collection period in the milestones accordingly, without further postponement of the final report (Q3 2023). The MAH contacted CPRD to confirm next steps for data extraction and validation study rerun. CPRD required that the MAH submits a new protocol to the CPRD review committee before requesting the new datasets and re-running the validation study. This is due to the change of dataset from CPRD GOLD to CPRD GOLD and CPRD Aurum, and the change of the observational period. The MAH submitted a new protocol to CPRD in April 2023 and expected to receive approval and the new datasets in Q3 2023. However, the actual process from application submission to data access took almost 12 months and the final data cut was eventually delivered in March 2024. The identification of new potential SCD cases as well as the initiation of validation activities have been completed in Q2 2024.

The validation of the diagnosis and SCD cases ended in Q2 2020 in Spain and expected to end in Q3 2024 in the UK. There is no validation study in Sweden. This study period is expected to allow for sufficient follow-up (long-term safety assessment) for those enrolled during the first period after linaclotide launch and for any subpopulations of interest (those with increased risk of SCD) to have the opportunity to accrue a sizable number of subjects for descriptive purposes. Please refer to Section 9.5 *Study Size* and Section 9.7 *Data Analysis* below.

[figure not shown]
The IBS-C cohort entry date for each cohort member will be defined as the date IBS-C criteria are first fulfilled or 01 February 2013 in Sweden, 13 May 2013 in the UK, and 01 September 2014 in Spain (linaclotide launch dates), whichever is the latest.

The follow-up period for each study subject in the IBS-C cohort will be from the cohort entry date to the earliest of the following (end of follow-up date; one day is the minimum follow-up (Figure 1):

- End of the study period
- Disenrollment from the database (date of transfer out of the practice or the PCP or Sweden)
- Date of last data collection for the practice
- Death
- Index date

The baseline period is the ≥ 12 -month period before IBS-C cohort entry date.

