9.7.2 COHORT ANALYSES

9.7.2.1 CRUDE INCIDENCE OF DIARRHOEA AND CRUDE INCIDENCE OF SEVERE COMPLICATIONS OF DIARRHOEA

Exposure to linaclotide and other risk factors (e.g., laxatives) will be ascertained from the prescription information recorded in the databases. Person-time at risk (person-years and person-weeks) for developing complications of diarrhoea will be used to compute the incidence and incidence density rates among patients in the IBS-C cohort.

Crude incidence density rates (person-time incidence rates) for the full cohort of patients with IBS-C will be graphically displayed over the follow-up period since cohort entry date, to ascertain if rates are homogeneous over time. Crude incidence density rates for sub-cohorts, defined by exposure to potential risk factors for experiencing SCD (e.g., current users of linaclotide), will also be graphically displayed over time since the first treatment prescription. These figures will guide whether the follow-up periods should be broken into several intervals with different incidence density rates of diarrhoea complications (based on the clinical development programme of linaclotide, diarrhoea has been observed to be more frequent early in treatment) or not. Additionally, the first six months after linaclotide launch will be studied separately, since patients with prevalent IBS-C who are exposed to linaclotide during this period

could have more severe cases of IBS-C, have exhausted other treatment options, and have a different risk profile than incident patients with IBS-C.

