9.7.2.2 RISK OF SEVERE COMPLICATIONS OF DIARRHOEA

If the validation results of cases is satisfactory (positive predictive value of EMRs $\geq 95\%$ and negative predictive value $\geq 99\%$), then information from the whole cohort would be used to estimate the incidence of SCD in the cohort of IBS-C patients, as well as the relative risks of SCD and the exposures of interest (mainly exposure to linaclotide) using the Cox proportional hazard model. Additionally, the nested case-control analysis will be conducted, and conditional logistic regression will be used as indicated in Section 9.7.3.1.

Alternatively, if the validation results show positive predictive value of EMRs $< 95\%$ or negative predictive value $< 99\%$, then only the nested case-control analysis will be conducted, and conditional logistic regression will be used in place of Cox regression.

The corresponding regression models will be used to identify risk factors associated with risk of SCD. Multivariate regression models will be fitted to identify the effects of various baseline variables on the probability of having SCD. A set of 10 to 20 plausible candidate models will be proposed and fitted to the data. Models will be ranked according to Akaike's Information Criterion (AIC) and the best model will be selected. If several models prove to perform well, these will be averaged to produce a final model. Some iteration between choosing candidate models and data analysis will likely be necessary: in the case of Cox regression, due to the need to check that the proportional hazards assumption holds for each candidate model, and in all scenarios due to the iterative nature of the information theoretic model-building approach.

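### About 35% of the UK window follows 1 March 2020, and with no calendar split in the crude rates a change in recording may be read as a change in risk over follow-up

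*Protocol*

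**What the plan says.** **Window.** Section 9.2.1.4 of the protocol starts the cohorts on "01 February 2013 in Sweden, 13 May 2013 in the UK, and 01 September 2014 in Spain (linaclotide launch dates" and closes them as follows: "The end of data collection has been extended to November 2023 in the UK, and December 2018 in Sweden and in Spain". Section 6 gives the UK end dates by data set: "20 October 2023 for CPRD Aurum, 17 November 2023 for CPRD GOLD 31 March 2021 for HES APC 31 October 2020". The last of these dates belongs to HES OP; the same cell gives 31 March 2020 for HES AE.

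**Pandemic.** Section 4.10 blames a COVID-19 shutdown for the poor response to the GP questionnaires available from February 2020. It reports that questionnaire studies were still paused in Q4 2021 because of a "shortage of primary care clinical staff in the UK to continue focusing their resources on supporting COVID-19 activities", and that the service had reopened in Q2 2022. These remarks explain delays. The limitations in Section 9.9 do not mention the pandemic.

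**Rates.** Section 9.7.2.1 computes crude incidence and incidence density. Full-cohort rates "will be graphically displayed over the follow-up period since cohort entry date, to ascertain if rates are homogeneous over time"; sub-cohort rates are plotted by time since first prescription. The figures guide whether follow-up is divided into intervals. The first six months after launch are examined separately; no other calendar division is named.

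**Model.** If validation succeeds, Section 9.7.2.2 estimates relative risks "using the Cox proportional hazard model". It leaves the candidate models open, and the variable list in Section 9.3.2 does not include calendar period.

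**The concern.** A plot against time since entry answers whether risk changes with time only if recording is stable in calendar time. In the UK there are two reasons to doubt that. One is documented: three hospital feeds stop between March 2020 and March 2021, although hospitalisation due to diarrhoea is itself an SCD criterion (Section 9.2.1.2). The other is plausible but not quantified in the protocol: primary care was under strain, and much of the diarrhoea and SCD coding comes from GP records.

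At stake are the crude UK diarrhoea incidence, which is an unconditional objective in Sections 4.3 and 8.2, the crude UK SCD rates if validation allows them, and the shape of the full-cohort curve. An average over periods with different recording describes neither period. A step caused by recording could also be taken for a late fall in risk.

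**Working it through.** **Inputs.** UK start 13 May 2013 (9.2.1.4). UK end 20 October 2023 for Aurum and 17 November 2023 for GOLD (6). HES AE, OP and APC end dates (6). Questionnaire service reopened Q2 2022 (4.10), taken as 30 June 2022. The cut at 1 March 2020 is a choice made here, not a protocol date; it sits close to the early-2020 questionnaire round and to the end of HES AE.

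**Step 1: the plan's own figure.** 13 May 2013 to 20 October 2023 is 3,812 days (10.44 years); to 17 November 2023 it is 3,840 days (10.51 years). Both agree with the stated "approximately 10 years in the UK".

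**Step 2: share of the window after each date.**

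| From | Aurum | GOLD |
|---|---|---|
| 1 March 2020 | 1,328/3,812 = 34.8% | 1,356/3,840 = 35.3% |
| End of HES AE, 31 March 2020 | 34.1% | 34.5% |
| End of HES OP, 31 October 2020 | 28.4% | 29.0% |
| End of HES APC, 31 March 2021 | 24.5% | 25.0% |

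March 2020 to June 2022 alone is 851 days, or about 22% of either window.

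**Step 3: effect on the overall crude rate.** If a share w of person-time has recorded rates lower by a fraction f, the overall rate is multiplied by 1 − w × f. Neither w nor f is in the documents. Calendar share stands in for w, and f is assumed.

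- Fall ending mid-2022 (w = 0.22): f = 0.20 lowers the rate by 4.4%; f = 0.50 by 11%.
- Fall lasting to the end (w = 0.35): f = 0.20 lowers it by 7%; f = 0.50 by 17.5% (17.7% with w = 0.353).

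With a person-time share anywhere from 0.20 to 0.45 and f from 0.10 to 0.50, the multiplier runs from 0.98 to 0.775.

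**Step 4: effect on the curve.** From 13 May 2013 to 1 March 2020 is 2,484 days, or 6.8 years. Patients prevalent at launch enter on the first date, so their follow-up time is calendar time and everything past 6.8 years is after the cut. For incident patients the later period is spread over all follow-up times.

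Take f = 0.30 lasting to the end, half the cohort prevalent, uniform incident entry and no loss to follow-up, with T = 10.44 and C = 6.80. At follow-up time y, prevalent patients have weight 0.5 and relative rate 1 (0.70 if y > C). Incident patients have weight 0.5 × (T − y)/T and relative rate 1 − 0.30 × (T − max(C, y))/(T − y). At mid-year points the combined relative rate goes from 0.95 down to 0.92 over years 1 to 7, then is 0.70 in years 8 to 10, with no true change in risk. If the fall ended in June 2022, the dip in prevalent patients would run from 6.8 to about 9.1 years ((2,484 + 851)/365.25) and then recover.

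**Step 5: effect on a rate ratio.** With w = 0.35 and a true ratio of 2, the crude ratio stays at 2.00 if linaclotide use is equally common in both periods. If use rose from an assumed 0.5% to 1%, falls of 10% to 50% give crude ratios of 1.97 to 1.79. These are crude ratios, not Cox estimates.

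**The case against.** The strongest reply is that the pandemic text concerns questionnaire logistics only. That is correct. A reader might infer that GP recording of diarrhoea and SCD did fall, or that UK rates drift by construction. The documents do not say so: no consultation or coding figure is given, the 20-50% falls are assumptions, and Q2 2022 is only the date on which a questionnaire service reopened. Only the ending of the hospital linkage is a documented change in ascertainment, and Section 9.9 already acknowledges in part that differing linkage periods may understate SCD. Nor are outcomes recorded solely by GPs, since HES and ONS contribute while they last.

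A reader might also infer that the plan disregards calendar time altogether, or that the Cox hazard ratio is biased. Neither is supported. The launch period is analysed separately. Section 9.7.2.2 fixes neither time scale nor covariates, and the statistical analysis plan, which is not shown, may include calendar period. Comparisons among patients prevalent at launch are calendar-matched on a time-since-entry scale, and Step 5 shows that the crude ratio moves only if exposure differs between periods; the protocol does not establish that it does.

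The reach is limited too. The case-control odds ratio, the first-listed objective, draws controls from the risk set at the case's index date (Section 9.2.1.3) and is therefore matched on calendar time. The Cox model and SCD incidence depend on the validation result. The follow-up intervals are applied to linaclotide sub-cohorts by time since first prescription, so the step at 6.8 years does not carry over directly. The longer UK window was a PRAC request, which argues against discarding later data. No objective compares countries, so an additional run on a common calendar window is optional.

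What this leaves untouched is that crude UK rates and the full-cohort curve cannot separate calendar change from follow-up time, and nothing in the protocol asks for the split that would.

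**Conclusion.** The concern holds for the UK crude diarrhoea and SCD rates and for the full-cohort display over follow-up. About 35% of the UK calendar window lies after 1 March 2020; HES coverage ends within that part, and the protocol itself reports disruption to primary care there. A change in recording may be read as a change in risk with longer follow-up.

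The size is not known from the documents. On the stated assumptions the overall UK rate would be 4-11% or 7-18% too low, depending on how long a 20-50% fall lasted and on calendar share being a fair proxy for person-time. For the Cox model this is a precaution, not a demonstrated bias. The nested case-control odds ratio is not affected in this way.

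**What to change.** - **Section 9.7.2.1:** report UK diarrhoea and SCD incidence rates separately before and from 1 March 2020. Show the UK follow-up curves with and without person-time from that date before deciding on intervals.
- **Section 9.7.2.2:** stratify any UK Cox model by calendar period as a time-varying stratum, splitting each patient's follow-up at the period boundary.
- **Section 9.9:** name the pandemic as a possible cause of altered recording, and extend the existing remark on linkage periods to say that HES ends in 2020-2021 while CPRD follow-up continues to late 2023.

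All of this uses data already held. The cost is some extra tabulation and slightly wider confidence intervals for the split rates.

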4.9 DATA ANALYSES

Country-specific analyses will be conducted, and the heterogeneity of the results will be tested. If heterogeneity is not confirmed, then a pooled analysis aggregating data for all three countries will be conducted and country effect will not be assessed.

Patient characteristics at cohort entry date will be described for the full cohort of patients with IBS-C, as well as incidence rate of diarrhoea.

If the results of the validation of cases are satisfactory positive predictive value of EMRs in the UK and Spain $\geq 95\%$ and negative predictive value $\geq 99\%$, then information from the whole cohort will be used to estimate incidence and incidence density rates for those groups of patients with IBS-C prescribed linaclotide and those who are potentially at increased risk of SCD and prescribed linaclotide. The crude incidence of diarrhoea and of severe complications of diarrhoea will be described by calculating the proportion of patients with IBS-C experiencing diarrhoea and SCD, respectively, and their associated 95% confidence intervals (CIs). Crude incidence density rates of SCD will be also calculated.

Additionally, the hazard ratios of SCD and the exposures of interest (mainly prescription of linaclotide) will be estimated using Cox proportional hazard models. ORs of SCD and the same exposures of interest will be estimated using data from cases and matched controls by applying conditional logistic regression analysis.

If the results of the validation of cases in the UK and Spain are not satisfactory (positive predictive value of our outcome algorithm in the UK and Spain $< 95\%$ or negative predictive value $< 99\%$), only the nested case-control study will be performed and ORs of SCD and the same exposures of interest will be estimated using data from cases and matched controls by applying conditional logistic regression analysis.

The goal is to assess SCD among patients who were treated with linaclotide, were ≥ 65 years old, and had history of hypertension, diabetes or cardiovascular disease diagnostic codes (i.e., SCD occurrence is the outcome variable [yes/no]. and the independent variables of main interest are whether the patient has a prescription for linaclotide, a prescription for laxatives, the patient is ≥ 65 years old, and the patient has hypertension, diabetes, or cardiovascular disease diagnostic codes, all of them at index date, or not, controlling for potential confounders).

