The crude incidence of diarrhoea and the crude incidence of SCD in the full cohort of patients with IBS-C will be described by calculating the proportion of patients experiencing at least one episode of diarrhoea and the proportion of patients experiencing at least one episode of SCD, as well as their corresponding 95% CIs. The crude incidences of diarrhoea and of SCD in the sub-cohorts of patients with prescriptions of linaclotide will be described by calculating the proportions of patients experiencing diarrhoea or experiencing SCD, respectively, among those at risk for each of the time intervals (as determined graphically) since first treatment prescription, as well as the corresponding 95% CIs. Crude incidence density rates (person-time incidence rates) will also be computed with their corresponding 95% CIs. The incidence of SCD will be assessed separately for death subsequent to diarrhoea (≤ 45 days after diarrhoea diagnosis date) due to the seriousness of this complication (deadly SCD).

All incidence and incidence density rates will also be calculated separately for those groups of patients with increased risk of SCD as defined in the objectives: patients ≥ 65 years and patients with hypertension, diabetes, or cardiovascular disease diagnostic codes.

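### Full-cohort crude incidence is defined as a proportion with no time horizon, although follow-up runs from one day to 50 months, 68 months or about 10 years depending on country

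*Protocol*

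**What the plan says.** Section 9.7.2.1 describes the crude incidence of diarrhoea and of SCD in the full IBS-C cohort by "calculating the proportion of patients experiencing at least one episode of diarrhoea and the proportion of patients experiencing at least one episode of SCD", each with a 95% CI. Section 4.9 defines crude incidence the same way. Neither gives a time point.

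Section 9.2.1.4 states that "the study period will include 50 months in Spain, approximately 10 years in the UK and 68 months in Sweden" and that "one day is the minimum follow-up". Follow-up also ends at leaving the database, last data collection, death or the index date. Section 9.7 plans country-specific analyses first and pooling if heterogeneity is not confirmed.

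Three other statements bear on the point:

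- Section 9.7.2.1 adds that "Crude incidence density rates (person-time incidence rates) will also be computed with their corresponding 95% CIs", and plans plots of these rates over follow-up.
- For linaclotide users, the same section takes proportions "among those at risk for each of the time intervals (as determined graphically) since first treatment prescription".
- On which events the person-time measures cover, section 9.7.2.1 says "Person-time at risk (person-years and person-weeks) for developing complications of diarrhoea will be used to compute the incidence and incidence density rates". Section 4.9 says "Crude incidence density rates of SCD will be also calculated", but for the full cohort it also promises patient characteristics "as well as incidence rate of diarrhoea".

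**The concern.** A proportion of patients with at least one event depends on the event rate and on how long patients were observed. Here the observation windows differ more than twofold between countries. Prevalent patients enter at launch, incident patients enter throughout, and patients leave for several reasons. Without a horizon, the percentage does not answer the question of risk by when.

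Describing the crude incidence of diarrhoea in the IBS-C cohort is an objective in sections 4.3 and 8.2, and this proportion is its named measure. Three things are at stake:

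- Country-specific percentages could differ through follow-up alone.
- A pooled percentage would mix windows of about 4, 6 and 10 years.
- The full-cohort percentage would share no horizon with the linaclotide percentages, which are given per interval since first prescription.

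**Working it through.** The protocol states no expected long-term incidence, so there is no figure of its own to reproduce. The check asks how far the crude proportions would differ if the true rate were identical everywhere.

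**Inputs**

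- Windows T, from section 9.2.1.4: Spain 50/12 = 4.17 years, Sweden 68/12 = 5.67 years, UK 10 years. Counting from the stated launch dates to the stated end dates gives slightly longer windows: 51–52 months, 70–71 months and 10.4–10.5 years. The stated figures are used below. With a UK window of 10.5 years, the main ratio is 2.11 instead of 2.04.
- Rate L, assumed. Section 9.5 gives about 3% with diarrhoea on placebo and 19.6% on linaclotide, in trials of 12 and 26 weeks. As constant yearly rates:
  - 3% over 26 weeks: −ln(0.97)/0.5 = 0.061
  - 3% over 12 weeks: −ln(0.97)/(12/52.18) = 0.132
  - 19.6% over 26 weeks: −ln(0.804)/0.5 = 0.436
- Loss rate c, assumed: 0, 0.05, 0.10 or 0.20 per year. The protocol gives no follow-up distribution.

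**1. Everyone followed for the whole window.** P = 1 − exp(−L·T)

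| L per year | UK | Spain | UK/Spain |
|---|---|---|---|
| 0.001 | 1.0% | 0.4% | 2.39 |
| 0.01 | 9.5% | 4.1% | 2.33 |
| 0.05 | 39.3% | 18.8% | 2.09 |
| 0.061 | 45.6% | 22.4% | 2.04 |
| 0.132 | 73.4% | 42.4% | 1.73 |
| 0.2 | 86.5% | 56.5% | 1.53 |
| 0.436 | 98.7% | 83.8% | 1.18 |

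Sweden at L = 0.061: 1 − exp(−0.061 × 5.67) = 29.2%.

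**2. Entry spread uniformly over the window.** P = 1 − (1 − exp(−L·T))/(L·T). The UK/Spain ratio is 2.15 at L = 0.061 and 1.93 at L = 0.132.

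**3. Equal exponential loss in both countries.** P = L/(L + c) · (1 − exp(−(L + c)·T)), with L = 0.061

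| c per year | UK | Spain | UK/Spain |
|---|---|---|---|
| 0.05 | 36.8% | 20.3% | 1.81 |
| 0.10 | 30.3% | 18.5% | 1.64 |
| 0.20 | 21.6% | 15.5% | 1.40 |

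Combining the higher rate of 0.132 with c = 0.20 gives 1.29.

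**4. Unequal loss.** Take L = 0.061, with c = 0.20 in the UK and none elsewhere. The UK proportion is 0.061/0.261 × (1 − exp(−0.261 × 10)) = 21.6%, against 22.4% in Spain and 29.2% in Sweden. The country with the longest window then shows the lowest percentage.

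**5. Person-time rate.** Under a common constant rate, expected events divided by person-time equals L in every country, so the UK/Spain ratio is 1.00 in all these scenarios.

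**The case against.** The strongest reply is that the plan already contains the remedy. Section 9.7.2.1 adds person-time rates with 95% CIs and plots them over follow-up, and step 5 shows that these are free of the distortion under a constant rate. A reader might infer that the plan offers only a bare proportion. It does not.

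The reach is also limited. The SCD incidence objectives in section 8.2 concern first-time linaclotide users, whose proportions are taken among those at risk in each interval, and SCD incidence depends on the validation result. So the full-cohort diarrhoea objective is the one that rests on this proportion. A reader might infer that censoring within the linaclotide intervals is ignored, but the protocol does not say how the number at risk is formed, and that detail may sit in the SAP. A reader might also fear that the linaclotide comparison is distorted. That comparison uses Cox regression or conditional logistic regression with risk-set controls, and neither uses the proportion.

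Finally, a factor of two, or a fixed ordering by window length, is not a necessary consequence. Both depend on assumed rates and follow-up, and step 4 breaks the ordering.

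All of this stands, and it makes the point smaller. It does not remove it. The rates are an additional measure, while the horizon-free proportion remains the definition of crude incidence and carries its own CI. A rate also does not give a risk by a stated time, which is useful when section 9.7.2.1 itself expects diarrhoea to be more frequent early in treatment. Nor is it clear that the rates cover diarrhoea: one sentence in section 9.7.2.1 ties person-time to complications, and section 4.9 names density rates for SCD while promising an incidence rate of diarrhoea separately.

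**Conclusion.** The point holds as an inexpensive improvement to a descriptive objective. The protocol fixes an estimator with no time frame for cohorts observed over very different windows. The resulting percentages cannot be compared between countries, cannot be given a time frame when pooled, and cannot be set beside the interval-based linaclotide percentages.

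At one common constant rate, the UK/Spain ratio is roughly 1.4 to 2.4 at low-to-moderate rates: 1.73 to 2.39 for 0.001 to 0.132 per year with full follow-up, and 1.40 to 1.81 at 0.061 per year with equal loss of 0.05 to 0.20 per year. It falls to about 1.2 at 0.436 per year, and unequal loss can change the ordering. These sizes rest on assumed constant rates and assumed loss, because the protocol gives neither a long-term diarrhoea rate nor a follow-up distribution.

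**What to change.** In sections 9.7.2.1 and 4.9:

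- Report full-cohort crude incidence of diarrhoea and of SCD as cumulative incidence at pre-stated horizons, the same for the full cohort and the linaclotide sub-cohort (for example 12 weeks, 26 weeks, 1 year and 3 years). Measure from cohort entry or first linaclotide prescription respectively.
- Estimate it by Kaplan-Meier, or by Aalen-Johansen with death as a competing event where death is not itself the outcome. Give it by country with 95% CIs.
- Keep the person-time rates, and state that they cover diarrhoea as well as SCD.
- If the simple proportion is kept, report it with the follow-up distribution for each country.

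This needs no new data, only a change of wording and standard SAS procedures. The downside is slightly more analysis work, and the percentage ever affected is no longer the headline figure.
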